# 11.5 Statistical Analysis of Secondary Objective 1.2.4 Neuroimaging

Objective: Estimate and compare the response of residual tumor and the incidence and severity of structural, functional and vascular effects of normal brain in children and young adults with ependymoma after treatment with a second course of irradiation using specific methods of diffusion, contrast-enhancement, vascular and functional neuroimaging, and explore the association between these and other measures of CNS effects and clinical and treatment factors. Determine the time course of white matter tract injury and recovery post irradiation and the association between imaging metrics derived from serial quantitative neural imaging and radiation dosimetry as well as neuro-cognitive outcomes.

Mixed effect models will be used to estimate and compare the structural, functional and vascular effects over time of normal brain and residual tumor in children and young adults with ependymoma after treatment with a second course of irradiation based on comprehensive imaging from MTR, DTI, DSC and SWI etc. Associations of those changes in the brain with other measures of CNS effects and clinical and treatment factors will be investigated using mixed effects models as well. The time course of white matter tract injury and recovery post irradiation by MTR and DTI will be described graphically and fitted by mixed effect models. The association between those quantitative neural imaging measurements change and radiation dosimetry/neuro-cognitive outcomes will be explored by mixed effect models.

Based on the number of tests performed to address this secondary objective, adjustments for multiple comparisons will be made to mitigate over interpreting exploratory findings. After the acquisition of four DTI/MT examinations in 15 patients in each stratum (a total of at least 45 examinations), interim analysis of MT imaging data will be performed and reported at an appropriate scientific meeting, as well as to the CT-SRC. The investigational MT sequence will no longer be performed after 8/1/2020.

# 11.6 Statistical Analysis of Exploratory Objective 1.3.1 Avidity to FDG and C-MET

Objective: Estimate the avidity of ependymoma to F-fluorodeoxyglucose (FDG) and C-methionine positron emission tomography (IND # 104987) prior to

St. Jude Children's Research Hospital IRB NUMBER: Pro00004349

IRB APPROVAL DATE: 02/01/2023

IRB Approval date:

Rev. 3.2 dated: 1/19/2023 Protocol document date: 1/19/2023 radiation therapy and correlate change in avidity 12, 24 and 36 months after a second course of irradiation with tumor progression. Estimate the avidity of FDG-PET and MET-PET at baseline and compare those two by t test or Wilcoxon rank sum test based on the distribution of the variables. The association between tumor progression and avidity to FDG and to MET will be explored by Cox regression model by using PFS as response variable and avidity measurements as time dependent covariates, where clinical and demographics variables of interest may also be included in these models, if the number of events is sufficient to support such a multivariable analysis. The association between PFS and baseline avidity will be also investigated. In these survival models, nine events per covariate are required. We will describe necrosis based on MET/FDG descriptively and graphically. The association between necrosis findings based on MET/FDG and necrosis findings based on MRI will be explored by mixed effect model.

Based on the number of tests performed to address this secondary objective, adjustments for multiple comparisons will be made to mitigate over interpreting exploratory findings.

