# 6.9.3 Positron Emission Tomography

Positron emission tomography (PET) will be performed at the time of study entry, 12, 24, and 36 months after the start of radiation therapy. The objective of this study is to correlate PET findings with rate and pattern of failure. The interpretation will include degree of avidity (none, low, moderate, high) and qualitative change when reviewing follow-up studies. The following data will be acquired: 1) metabolic tumor volume at different SUV levels; 2) metabolic activity within MRI defined volumes (target volumes and solid, cystic and combined components); 3) minimum, maximum and mean SUV of the solid component, 4) SUV distributions of the metabolic tumor volume and MRI defined volumes at different time points; and 5) change in parameters over time.

F18-FDG PET will be obtained with the patient NPO for at least 6 hours. Images will be acquired in 3-D mode for 5-15 minutes, 1 hour after the administration of F18-FDG. Radiopharmaceutical dose will be 0.10-0.15 mCi/kg body weight (minimum: 2mCi per dose; maximum: 12mCi per dose). A non-contrast CT scan of the area of interest will be obtained immediately prior to the commencement of PET image acquisition.

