#### **6.9.4 MET-PET**

MET-PET participants will fast for at least 4 hours prior to the study. Patients are then injected intravenously with 20mCi/1.7 sq m body surface area of Cmethionine (maximum prescribed dose 20 mCi). The administered dose will be +/- 20% of the prescribed dose due to the rapid decay of C-methionine. For doses outside this range, physician documentation is required. A non-contrast CT scan of the area of interest will be obtained immediately prior to the commencement of PET image acquisition. Scanning may begin immediately for dynamic studies using a framing rate to be determined. For non-dynamic studies, scanning may begin ~ 5 minutes after injection for ~15 minutes. Acquired data are reconstructed into multiplanar attenuation and nonattenuation images using standard vendor supplied software.

PET Logistics: In the event of delays which cause the available activity to fall to less than 25% of the prescribed dose, then the decision to proceed will be based

> St. Jude Children's Research Hospital IRB NUMBER: Pro00004349

on factors such as ability to reschedule the patient in a timely manner, cyclotron chemistry availability, anesthesia resources, need to commence therapy, etc. The nature of the study allows flexibility. The study can be abbreviated and tailored so that the primary objective can be satisfied without sufficient activity to address the secondary objectives. Image analysis will be performed both qualitatively and semi quantitatively.

PET Analysis: Qualitative analysis will be conducted by the responsible investigators and will consist of visual inspection of the area suspected to contain tumor and comparison with uninvolved nearby tissue. The tumor will be compared with uninvolved brain and the uptake will be graded on a scale comparable to the following: 0=no detectable uptake; 1=uptake present but less than noninvolved background; 2= uptake approximately equal to background; 3=uptake greater than background. Semi-quantitative analysis will be performed include calculation of a standardized uptake value (SUV: activity in the region of interest normalized to participant weight and injected dose) by drawing a region of interest (ROI) over the area suspected to contain tumor.

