The one interim analysis, based on the work by Xiong et al, [298] will be conducted when 50% of the expected number of failures (67) for the 90 patients to be treated prospectively (assuming the alternative hypothesis) has been observed (~34 patients have failed). The planned interim analysis will occur at approximately 68% of the expected total "transformed information time," assuming the alternative hypothesis. Accrual will be suspended until all available information has been considered, if the observed nominal p-value is  $\leq 0.0582$ . At the final analysis, one would conclude that the prospective results are inferior to the retrospective results if the p-value is  $\leq 0.10$ . The log-rank comparisons will be stratified by three strata define above and the power should be retained [299]. With this design the actual significance level is 0.1089; the power is 0.7915 and the maximum probability of an interim decision being discordant with a decision that would be made by a final analysis is 0.05 (5%).

While the expected accrual to this trial is considerably greater than our historical experience, we expect that accruing 12 patients per year is realistic. Our current case review for re-irradiation includes approximately two chart review consultations per month. Patients treated to date include those previously irradiated in department or from our region. Based on institutional policy, patients cannot be accepted for treatment at St. Jude in the absence of a clinical protocol. Thus when this trial opens, we will begin to actively recruit patients for the trial. Furthermore, we have offers from a number of centers to collaborate in this effort. If accrual is not meeting expectations by the end of year 2, we will contact these centers to participate.

At the time of amendment #2, the study had been open for 4 years and we accured 53 patients. The accrual rate was approximately 10 patients/year and less than the 15 patients per year target (initial). We extended the accrual time by 3 years to reach the accrual goal and added a collaborative site.

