performed more frequently for patients with spinal metastatic disease or at the discretion of the treating physician. Lumbar puncture for CSF cytology may be waived with PI approval based on contraindication or if adequate evaluation was performed within 3 weeks of enrollment. MET PET and FDG-PET scans not performed at 12, 24 or 36 month evaluation may be performed at a subsequent follow-up evaluation. All METPET studies will be whole-body regardless of the presence or absence of metastatic disease at the time of enrollment. Patient must be > 3 years of age. For patients enrolled before August 30, 2019 Test will not be collected after July 1, 2020 \*\*Optional at the dicretion of the treating physician

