## Amendment 2.0

Research Test	Time Acquisition
MRI of Brain (research portion)	Baseline and 3, 6, 9, 12, 15, 18, 21, 24, 27 & 33
	(optional), 30, 36, 42, 48, 54, 60 months
Sleep Fatigue and Quality of Life	Baseline, each week during treatment and 3, 6, 9,
Questionnaires 	12, 15, 18, 21, 24, 30, 36, 42, 48, 54, 60 months
Serum Cytokine 	Baseline, week 3 & 6 during treatment and 12, 24,
	36, 48, 60 months
MET PET  & FDG PET 	Baseline and 12, 24, 36 month
Genomics 	Baseline
Neuropsychological Testing	12, 24, 48, 60 months
Human Performance Laboratory 	Baseline and 12, 24, 36, 48, 60 months
	, , , , , , , , , , , , , , , , , , , ,
Actigraphy 	Baseline and 12, 24, 36, 48, 60 months
rengrupny	Buseline and 12, 21, 30, 10, 00 months
Provocative Endocrine Testing 	Baseline
Trovocative Endocrine resting	Bascinic
I -41 -111 V	Describes
Lateral skull X-ray	Baseline
DEED A	
PET Activation 	Depending on feasibility and availability

<sup>1Performed only at St. Jude Children's Research Hospital. Collaborating sites will not participate in these tests.

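### The baseline FDG versus methionine comparison names an independent-samples rank test for readings taken in the same patients

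*Combined protocol and SAP*

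**What the plan says.** Section 11.6 opens its analysis with "Estimate the avidity of FDG-PET and MET-PET at baseline" and will then "compare those two by t test or Wilcoxon rank sum test based on the distribution of the variables". It names no paired test or within-patient model for this step. The mixed-effect model later in the section is for agreement between PET and MRI necrosis findings.

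The data come from one schedule. Section 6.9.3 says PET "will be performed at the time of study entry, 12, 24, and 36 months after the start of radiation therapy". Tables 6.0.1 and 6.0.2 mark both FDG-PET and PET-methionine at month 0, and Appendix III lists the two together at baseline. Nothing in the documents allocates a patient to one tracer.

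Two provisions make the pairing incomplete. The methionine row of the schedules carries a footnote, "Test will not be collected after July 1, 2020", which the FDG row does not. Appendix III (Amendment 2.0) says of both PET tests, among others, that "Collaborating sites will not participate in these tests".

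Avidity is read in several ways. Section 6.9.3 records "degree of avidity (none, low, moderate, high" and also SUV and metabolic-volume measures. Section 6.9.4 has a 0 to 3 uptake grade ("0=no detectable uptake; 1=uptake present but less than noninvolved background", and so on) and an SUV. Section 11.6 does not say which reading is compared.

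**The concern.** Two readings of the same patient's tumor are not independent. The Wilcoxon rank sum test assumes two independent groups; its counterpart for pairs is the signed-rank test. An unpaired test judges the tracer difference against the full spread between patients, when the relevant variation is the smaller within-patient spread. With positive correlation, a real difference between the tracers is then more likely to be missed.

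The choice between the two tests is left to the data. If an ordered grade is what is compared, the rank branch is the natural one, and that is the branch with no paired reading.

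The analysis set is also open. If every FDG scan were set against the methionine scans done before the July 2020 cut-off, the contrast would mix a tracer difference with a difference between earlier and later patients.

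**Working it through.** The plan gives no sample size, power or significance level for this comparison, so there is no figure to reproduce. The check is whether the test fits the data, followed by an illustration of the cost.

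**Inputs.** From the documents: both tracers at month 0 (Tables 6.0.1 and 6.0.2), and enrollment of 53 at Amendment 2 (section 11.1: "the study had been open for 4 years and we accured 53 patients"). The 53 is used only as an illustrative number of pairs; it counts enrolled patients, not patients with both scans. Assumed, because the documents are silent: two-sided 5%, equal SDs, a true shift d = 0.4 SD, correlation ρ = 0, 0.3, 0.5, 0.7, and 20, 30 or 53 pairs.

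**By formula (z approximation).**
- The unpaired standard error exceeds the paired one by the factor 1/√(1 − ρ) = 1.00, 1.20, 1.41, 1.83.
- True error of an unpaired test at nominal 5%: 2·[1 − Φ(1.96/√(1 − ρ))] = 5.0%, 1.9%, 0.6%, 0.03%.
- Paired power: Φ(d√n/√(2(1 − ρ)) − 1.96). For n = 53 and ρ = 0.5: 0.4 × 7.28 = 2.91; 2.91/1.00 − 1.96 = 0.95; power 83%.
- Unpaired power on the same data: Φ((d√(n/2) − 1.96)/√(1 − ρ)). For n = 53 and ρ = 0.5: (2.06 − 1.96)/0.707 = 0.14; power 56%.

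**By simulation of the named tests** (6,000 bivariate normal data sets per cell; simulation error about 0.6 percentage points). Power at d = 0.4 SD:

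| Pairs | Test | ρ = 0 | 0.3 | 0.5 | 0.7 |
|---|---|---|---|---|---|
| 53 | rank sum | 51% | 51% | 51% | 52% |
| 53 | signed-rank | 50% | 66% | 79% | 95% |
| 30 | rank sum | 30% | 28% | 25% | 20% |
| 30 | signed-rank | 30% | 42% | 54% | 76% |
| 20 | rank sum | 22% | 19% | 15% | 12% |
| 20 | signed-rank | 21% | 29% | 38% | 57% |
| 53, four-level grade | rank sum | 47% | 47% | 45% | 46% |
| 53, four-level grade | signed-rank | 47% | 58% | 68% | 86% |
| 53 | t test, unpaired | 53% | 54% | 53% | 56% |
| 53 | t test, paired | 53% | 68% | 81% | 96% |

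The four-level grade cuts the same values at the first tracer's quartiles, corrects for ties and drops zero differences in the signed-rank test.

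With no true difference and 53 pairs (continuous readings), the rank sum test rejects in about 5%, 2.2%, 0.7% and 0.1% of data sets at the four correlations. The signed-rank test stays between 4.5% and 5.6% throughout.

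**Sensitivity to the effect size** (3,000 data sets per cell), rank sum against signed-rank power:
- 53 pairs, ρ = 0.5: 53% and 80% at 0.4 SD; 92% and 99% at 0.6 SD; 99.6% and 100% at 0.8 SD.
- 53 pairs, ρ = 0.3: 88% and 94% at 0.6 SD.
- 20 pairs, ρ = 0.5: 73% and 92% at 0.8 SD.

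**The case against.** The strongest reply is that little rests on this comparison. Objective 1.3.1 asks for avidity before irradiation and for the relation of its change to progression. It does not ask which tracer is more avid, and the Cox models that serve the objective are untouched. That stands, and it is why the point is minor.

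Second, the t test could be read as paired. That is fair: the clear error is the rank sum test, and the t test only needs to be specified. The unpaired t figures above apply only if it is run unpaired.

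Third, use of the rank branch is an inference. SUV readings are available, and the 0 to 3 scale sits under the methionine heading, so its use for FDG is not explicit. This is true, but it also shows that section 11.6 must name the reading.

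Fourth, the size of the loss is uncertain. The 0.4 SD shift is assumed, and larger shifts shrink the gap. Usable pairs could be well below 53, since surgery may precede enrollment (section 4.1) and 68% of the historical cohort had gross total resection (section 11.0). Section 11.6 also promises multiplicity adjustment, so power at nominal 5% is not the power of the planned analysis. All of this limits the illustration, not the mismatch between test and data.

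Fifth, the absence of excess false positives might depend on equal spread. With one tracer's SD twice the other's and correlations from 0 to 0.5, the rank sum error still did not exceed the nominal level beyond simulation error.

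**Conclusion.** The concern holds. The rank sum test as written does not suit readings taken in the same patients, and the t test should be stated to be paired. The effect is conservative: with positive within-patient correlation, power is lost and false positives fall below 5%. Under the assumptions of 53 pairs, a 0.4 SD shift and correlation 0.5, power is about 51% where the signed-rank test would have 79%. The loss is nil at zero correlation, small when many pairs meet a large shift, and still material with 20 pairs. The documents do not fix the correlation, the shift or the number of pairs, so the actual loss is unknown. Severity is minor: one comparison within an exploratory aim, with no bearing on the primary or safety analyses.

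**What to change.** In section 11.6, specify a paired t test or a Wilcoxon signed-rank test in patients who have both baseline scans. Name the avidity reading compared, using the same reading for both tracers, and report the number of pairs.

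This costs one sentence of SAP text and no new data. Patients with only one tracer, such as those with FDG alone after the July 2020 cut-off, leave this comparison but can still be described for the tracer they had. If the team prefers to keep them, a mixed model with a patient effect is an alternative within-patient analysis.

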#### 4.0 TREATMENT AND PLAN STRATIFICATION

#### 4.1 Overview

Patients will be enrolled on this protocol at St. Jude Children's Research Hospital (SJCRH) if they meet the eligibility criteria outlined in section 3.0. Patients may be enrolled before or after surgery performed at the time of recurrence. Enrollment prior to surgery is preferred to prospectively obtain peri-operative information about surgical morbidity and to facilitate the acquisition of tissue for biology studies. This protocol allows for co-enrollment on other protocols for recurrent ependymoma including those that might administer chemotherapy after irradiation. Chemotherapy concurrent with radiation therapy will not be allowed. Patients will be jointly evaluated by treatment teams representing neuro-oncology, radiation oncology and neurosurgery.

In the event that collaborative sites are allowed to join this trial, SJCRH will not be financially responsible for the cost of surgery, radiation therapy or follow-up for patients enrolled at collaborative sites. All patients are expected to undergo clinically indicated follow-up measures at the enrolling institution or at their routine point of care. Collaborative sites are expected to perform the research outlined in the protocol unless otherwise specified. The PI and protocol team at SJCRH will establish appropriate and legal (HIPAA) compliant communication with the enrolling institutions and the routine point of care for each patient.

Patients will be considered for enrollment if they have progressive disease after prior therapy that included surgery and focal irradiation with or without chemotherapy. There is no limit regarding the time interval from initial treatment failure to enrollment on this protocol which means that patients may choose other forms of therapy prior to enrollment on this protocol. Multiple episodes of progression will be allowed. The most common enrollment scenario will be the

Rev. 3.2 dated: 1/19/2023 IRB Approval date: St. Jude Children's Research Hospital IRB NUMBER: Pro00004349

patient who has been diagnosed with asymptomatic recurrence noted on surveillance neuroimaging. This patient will be consented for the study and will undergo pre-operative evaluations. Post-operatively, the studies necessary for treatment planning and to assess the impact of resection will be performed or repeated.

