It is expected that some patients will have surgery for local recurrence or metastasectomy prior to enrollment. Enrollment before surgery is preferred to facilitate tumor-related imaging studies, tissue procurement and baseline evaluation of neurological function. Regardless, studies performed prior to enrollment and tissue from any surgery performed prior to enrollment will be part of the protocol data set.

Patients will be enrolled if initial or post-irradiation pathology or imaging reports confirm a diagnosis of ependymoma or suggest a differential diagnosis that might include ependymoma. Limited tissue availability from initial and subsequent surgeries along with expanding efforts to sub-classify tumors may lead pathology reviewers to consider a range of diagnoses for which identical interventions and treatments would be considered. These patients will be enrolled after review by the principal investigator and treating physicians.

At the time of enrollment, patients will undergo extent of disease evaluation that will include MR imaging of the brain and spine and CSF cytology. To reduce cost and in consideration of the patient, the extent of disease evaluation may be waived with PI approval if a similar and adequate evaluation was performed within 3 weeks of enrollment. It should be noted that for patients who proceed directly to irradiation, specific sequences will be required for radiation therapy treatment planning of intracranial disease if not present in the prior extent of disease evaluation. For patients who undergo further surgery, extent of disease evaluation after surgery is required; only CSF cytology may be waived based on safety concerns or for patients with obvious neuraxis metastases noted on imaging.

Optimally, patients will undergo surgery to achieve minimal residual disease. It is our hope, but not required, that they will experience limited morbidity from surgery and proceed to irradiation within 12 weeks of last surgery. The pre- and post-operative neuroimaging and clinical assessments will be completed to satisfy the secondary objectives for the study, aid in the treatment planning process, and provide information for longitudinal assessment of toxicity.

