#### 6.0 REQUIRED EVALUATIONS, TESTS AND OBSERVATIONS

#### Instructions regarding the logistics of baseline evaluations

Surgery→enrollment→no surgery→ radiation therapy

If surgery was performed prior to enrollment and the patient does not require additional surgical intervention, similar to the preceding section, they should be enrolled on protocol and undergo baseline evaluation prior to radiation therapy.

Surgery→enrollment→surgery→ radiation therapy

Regardless of prior surgical history, patient who will undergo additional surgery should be enrolled on protocol and undergo baseline evaluation prior to surgery. If they are unable to complete the required baseline evaluations prior to surgery, partial evaluation will be accepted and the remaining baseline evaluations should be completed after surgery (i.e., partial evaluations prior to and following surgical intervention will be accepted). Investigators should consider repeating aspects of

IRB Approval date:

Rev. 3.2 dated: 1/19/2023 Protocol document date: 1/19/2023 St. Jude Children's Research Hospital

IRB NUMBER: Pro00004349

the baseline evaluation (e.g., diagnostic imaging, neurological examination, ophthalmology, etc.) that may be altered by surgery.

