# 6.9 Diagnostic and Investigational MR Imaging

#### 6.9.1 General Information

Diagnostic imaging will be performed at enrollment regardless of prior surgery history.

St. Jude Children's Research Hospital IRB NUMBER: Pro00004349

IRB APPROVAL DATE: 02/01/2023

IRB Approval date:

- (1) Investigational imaging may be performed at enrollment or deferred until after planned surgery.
-  Diagnostic imaging should be repeated when indicated after planned surgery and prior to radiation therapy.
- (3) Repeating the investigational imaging following planned surgery is not required if performed at the time of enrollment; however, attempted completion of the investigational imaging is expected prior to radiation therapy.

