\*Patient of childbearing potential requires a negative pregnancy test prior to starting treatment. (‡) should be repeated if clinically indicated following craniotomy. Imaging and clinical tests should be performed prior to radiation therapy; however, logistics may make it difficult to complete all exams prior to treatment. The principal investigator reserves the right to accept pre-irradiation testing within 16 weeks of the initiation of radiation therapy. PET-FDG and PET-methionine will also be done at time of progression or recurrence if prior to 24 months. Assessment/triage includes neck and abdomen circumference. #Edinburgh Handedness Inventory performed once. Patients who are unable to undergo standard audiometry may undergo ABR at the treating physician's discretion. Provocative screening will not be conducted for patients when the number of days off corticosteroids prior to the test date is less than the number of days on corticosteroids prior to discontinuance. MR spine may be performed more frequently for patients with spinal metastatic disease or at the discretion of the treating physician. Lumbar puncture for CSF cytology may be waived with PI approval based on contraindication or if adequate evaluation was performed within 3 weeks of enrollment. MET PET and FDG-PET scans not performed at 12, 24 or 36 month evaluation may be performed at a subsequent follow-up evaluation. All METPET studies will be whole-body regardless of the presence or absence of metastatic disease at the time of enrollment. Test will not be collected after July 1, 2020

Table 6.0.2 Evaluations at Baseline and Follow-up at St. Jude (Amendment 2.0)

Evaluations/Schedule 	Months after RT Start																
	0	3	6	9	12	15	18	21	24	27**	30	33**	36	42	48	54	60
Imaging																	
Diagnostic/Investigational	X	X	X	X	X	X	X	X	X	X	X	X	X	X	X	X	X
MR																	
MR Spine 	X				X				X				X		X		X
FDG-PET 	X				X				X				X				
PET-methionine 	X				X				X				X				
Lateral skull X-ray	X																
Bone Age/Q-CT/DEXA7	Х																
Clinical-Standard																	
Assessment/Triage	X	X	X	X	X	X	X	X	X	X	X	X	X	X	X	X	X
Physical Exam‡#	X	X	X	X	X	X	X	X	X	X	X	X	X	X	X	X	X
Lab: CBC‡	X	X	X	X	X	X	X	X	X	X	X	X	X	X	X	X	X
Lab: Chemistry‡	X	X	X	X	X	X	X	X	X	X	X	X	X	X	X	X	X
Lab: Endocrine Screen‡	X		X		X		X		X	X	X	X	X	X	X	X	X

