# Factors Associated with Outcome: Extent of Surgical Resection at Initial Recurrence

The following table shows the distribution of surgical resection with a gross total resection achieved in 68% of patients.

[figure not shown]
Extent of Surgical Resection or Metastasectomy								
Gross Total Resection (GTR)	34	68.0%						
Near Total Resection (NTR)	9	18.0%						
Sub Total Resection (STR)	7	14.0%						

[figure not shown]
Below are Kaplan-Meier estimates of distributions of PFS and OS by extent of surgical resection at initial recurrence. The Cox models following the figures suggest that patients for whom a gross total resection was achieved have better survival.

IRB Approval date:

Protocol document date: 1/19/2023

Rev. 3.2 dated: 1/19/2023

Cox Model of PFS for Extent of Surgical R	Resection
---	-----------

	Initi	Initial Disease Control in Years								
Neuropathology	≤ 1.22		1.22< - ≤		1.84< - ≤		3.53< - ≤			
at Recurrence			1.84		3.53		10.3	35	Totals	
	N	%	N	%	N	%	N	%	N	%
AEP	7	26.92	7	26.92	8	30.77	4	15.38	26	52.0
EP	4	22.22	2	11.11	4	22.22	8	44.44	18	36.0
FAEP	0	0	2	100.0	0	0	0	0	2	4.0
No Path	1	25.0	2	50.0	1	25.0	0	0	4	8.0
Totals	12	24.0	13	26.0	13	26.0	12	24.0	50	

		Parameter	Standard	Standard		95% Hazard Ratio	
		Estimate	Error	Pr > ChiSq	Ratio	Confide	ence Limits
GTR vs.	NTR +STR	-0.91550	0.42108	0.0297	0.400	0.175	0.914

Cox Model of OS for Extent of Surgical Resection											
	Parameter Standard Hazard 95% Hazard R										
	Estimate	Error	Pr > ChiSq	Ratio	Confidence Limits						
GTR vs.NTR+STR	-1.01384	0.47177	0.0316	0.363	0.144	0.915					

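### Baseline PET may be taken before or after resection with no visible tumour required, so the unadjusted avidity-PFS association in Section 11.6 may be biased toward low avidity looking favourable

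*Combined protocol and SAP*

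**What the plan says.** Section 11.6 estimates baseline FDG and methionine avidity, fits Cox models of PFS with avidity as a time-dependent covariate, and adds: "The association between PFS and baseline avidity will be also investigated". Clinical and demographic variables are optional and limited by a rule of nine events per covariate. Neither extent of resection nor scan timing is named.

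On timing:
- Section 6.9.3: "Positron emission tomography (PET) will be performed at the time of study entry, 12, 24, and 36 months after the start of radiation therapy".
- Section 4.1: "Patients may be enrolled before or after surgery performed at the time of recurrence". It adds: "It is expected that some patients will have surgery for local recurrence or metastasectomy prior to enrollment".
- Section 6.0 asks for baseline evaluation before any further surgery. If that cannot be completed, "partial evaluation will be accepted and the remaining baseline evaluations should be completed after surgery".
- Section 6.9.1: "Investigational imaging may be performed at enrollment or deferred until after planned surgery".
- Notes to Tables 6.0.1 and 6.0.2: "The principal investigator reserves the right to accept pre-irradiation testing within 16 weeks of the initiation of radiation therapy". This window is tied to irradiation, not to surgery.

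On scoring, the four-level reading in Section 6.9.3 starts at none, and the 0-to-3 scale in Section 6.9.4 has a zero for absent uptake. Section 2.7 mentions imaging visible residual tumour as an aim, but no section makes visible tumour a condition for the scan or the analysis.

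On resection, Section 11.0 describes the historical cohort "with a gross total resection achieved in 68% of patients" and reports a PFS hazard ratio of 0.400 for gross total versus lesser resection.

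**The concern.** The baseline scan shows an intact recurrence in some patients and an operated bed in others. If the bed is empty, the visual scales still allow a score, and that score is low. In those patients low avidity records that the tumour has been removed, not that it takes up little tracer.

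Extent of resection is then linked both to the avidity score and to PFS, so an unadjusted model mixes the two. Low avidity would tend to look favourable even if uptake carried no prognostic information, and the estimate of ependymoma avidity sought by Objective 1.3.1 would be diluted by scans without tumour. A related difficulty affects change in avidity: where surgery falls between the baseline and follow-up scans, a fall may reflect resection. Section 4.2 also allows residual tumour to be resected in the first 12 months after irradiation starts without this counting as progression.

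Section 2.7 says that what is learned will influence whether PET is used, so a misleading association would matter.

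**Working it through.** **1. The plan's own figure.** Section 11.0 gives, for PFS, a log hazard ratio of -0.91550 with standard error 0.42108.
- HR = exp(-0.91550) = 0.400.
- 95% CI = exp(-0.91550 ± 1.96 × 0.42108) = 0.175 to 0.914.
- z = 0.91550/0.42108 = 2.17, two-sided p = 0.0297.
- Gross total resection rate = 34/50 = 68%.

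All agree with the document.

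**2. Share of baseline scans without tumour.** Let f be the share of baseline PETs taken after surgery. The documents do not give f, so it is varied. If extent of resection is unrelated to scan timing (an assumption), the tumour-free share is 0.68 × f: 0% at f = 0, 13.6% at f = 0.2, 34% at f = 0.5 and 54.4% at f = 0.8.

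**3. Imbalance in resection.** Assume that a post-operative scan after gross total resection reads low, and that any other scan reads low with probability q. At f = 0.5 and q = 0.1:
- Low group: 0.34 + 0.66 × 0.1 = 0.406 of patients. Gross total resection among them: (0.34 + 0.34 × 0.1)/0.406 = 92%.
- Remaining group: 0.594 of patients. Gross total resection among them: 0.34 × 0.9/0.594 = 52%.

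**4. Effect on the hazard ratio.** Cox models were fitted to 40,000 simulated patients per scenario. The inputs were no true avidity effect, 68% gross total resection with HR 0.400, marginal 3-year PFS of 50%, constant hazards and follow-up of 2 to 5 years.

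| Post-operative share f | Spurious HR, low vs higher avidity (q = 0.1 to 0.3) |
|---|---|
| 0 | 1.00 |
| 0.2 | 0.81 to 0.89 |
| 0.5 | 0.70 to 0.76 |
| 0.8 | 0.56 to 0.61 |
| 1 | 0.42 to 0.46 |

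At f = 0.5 and q = 0.1, moving the resection effect across its confidence interval (0.175 to 0.914) moves the spurious HR from 0.53 to 0.98. In the same scenario with the resection HR at 0.400, adding extent of resection to the model moves the avidity HR from 0.70 to 1.01, against a true value of 1.

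**5. Room for the covariates.** Avidity, scan timing and extent of resection are three terms, needing 3 × 9 = 27 events. Section 11.1 expects 67 failures in 90 patients, and 67/9 allows 7 terms. At that failure rate, 27 events need 27 × 90/67 = 36.3, so about 37 patients with a usable scan. A piecewise-exponential check with the plan's hazards (0.233, then 0.056), 9 years of accrual, 2 further years and no dropout gives 70.0 failures under the alternative and 57.2 under the null, so 67 is not matched exactly. At 57.2 failures the plan's rule allows 6 terms, and about 43 patients would be needed (27 × 90/57.2 = 42.5).

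**The case against.** The strongest reply is that the protocol leans toward pre-operative baselines. Section 4.1 prefers enrolment before surgery and describes the commonest entrant as someone with recurrence found on surveillance imaging who then has pre-operative evaluations. Section 6.0 makes post-operative completion the fallback. The deferral in Section 6.9.1 sits under an MR heading, so applying it to PET is an inference. This stands: the post-operative share may be modest, and with none the bias vanishes. It does not close the gap, because patients operated on before enrolment are expected and their study-entry scan is necessarily post-operative.

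Second, the objective is exploratory, covariates are permitted and multiplicity adjustment is planned. That limits the consequence, but multiplicity adjustment does not address confounding, and an optional covariate that is not named may not be used.

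Third, a solid-component SUV is undefined after complete resection, so some patients may be missing rather than low. This is true of that measure. The visual scales still yield a score, and the plan does not say how such patients are handled.

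Fourth, the historical resection effect is imprecise, and Section 11.0 calls those analyses exploratory. This stands, and is why the range reaches 0.98.

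A reader might also infer stronger claims that the documents do not support:
- That neither scan measures ependymoma avidity. A pre-operative scan of an intact recurrence does.
- That 68% of 90, about 61 patients, have no tumour at baseline. That needs every scan to be post-operative. It also ignores that PET is done only at St. Jude (Appendix III) and that methionine PET stopped after July 1, 2020.
- That the resection HR of 0.400 carries over in full. It is attenuated unless nearly all scans are post-operative.
- That Section 11.6 models a fall from baseline as radiation response. Change is in the objective and is collected, but the specified model uses time-dependent avidity.

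**Conclusion.** The concern holds in limited form. Followed as written, Section 11.6 allows an empty tumour bed to count as low avidity and does not require adjustment for the resection that emptied it. The expected direction is toward low avidity looking favourable, provided that gross total resection is again associated with better PFS. The size is uncertain: no bias if all scans are pre-operative, a spurious HR of about 0.8 to 0.9 at a 20% post-operative share and 0.70 to 0.76 at 50%. These values assume the historical resection rate and effect, resection extent unrelated to scan timing, and post-operative scans after gross total resection reading low. Avidity may look prognostic for this reason; the documents do not show that it will. The primary objective, sample size and necrosis rule are unaffected.

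**What to change.** In Section 11.6:
- Estimate baseline avidity only in patients with tumour visible on the MRI concurrent with the PET, and report how many are left out.
- Classify each baseline PET as before or after resection.
- Make that class and extent of resection (gross total versus less, with indeterminate cases flagged) required covariates or strata in the avidity-PFS models. Apply the nine-events rule separately for FDG and methionine. PFS runs from the start of re-irradiation, so extent of resection before irradiation is known at time zero.
- For change in avidity, keep patients scanned only before surgery. Report change separately for those with and without surgery between the baseline and follow-up scans, counting resections after irradiation allowed by Section 4.2. Attribute change to irradiation only in those without intervening surgery.

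This needs analysis-plan wording and derived variables from scan dates, surgery dates, MRI and resection status, with no new scans. Section 4.2 warns that extent of resection will sometimes be indeterminate, hence the flag. The downside is fewer evaluable patients. Excluding everyone without a post-operative baseline from the change analysis would cost more, because Section 6.9.1 does not require investigational imaging to be repeated after surgery. The loss would then fall on the protocol's preferred pathway.
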